Trial Arm 1 VRT (intervention arm): VOG-based logic rules determine rapid triage pathway

- report includes direct device output (physiologic traces, quantitative measures) plus most likely diagnosis, category, and clinical trial care pathway (peripheral, equivocal, central) instructions
- the VOG results become part of the patient's clinical record

The roles of the ED provider in the care of patients in the VOG arm will be as follows:

- assess illness severity and appropriateness of the patient for VOG testing and the study protocol
- exclude obvious general medical conditions
- take over diagnostic decision-making for patients in whom VOG is equivocal (with consultant input, if available)
- intervene to deviate from VRT pathway if they are concerned about safety for patients in the VOG arm

Note: these are the same roles anticipated for ED providers if the VOG device were used for clinical practice

Trial Arm 2 Standard Care (control arm): usual ED care plus VOG exam, no VOG report generated

- no VOG automated interpretation or summary report will be generated; the computer-based randomization algorithm does not generate a VOG report or pathway using logic rules in the control (standard care) arm

The roles of the ED provider in the care of patients in the standard care arm will be as follows:

- assess illness severity and appropriateness of the patient for VOG testing and the study protocol
- exclude obvious general medical conditions
- all diagnosis, consultation, treatment, and disposition decisions will be made by the treating ED provider(s)

5.1.3 Expert Human VRT Double-Check: The VRT algorithm outputs in the intervention arm will be double-checked by expert neuro-otology fellows or faculty in real time to ensure accuracy; human judgment will “trump” VRT if there is disagreement (or if, for technical reasons, the real-time algorithm is not able to be generated – for example, as with internet connectivity problems or during development). The expert human double-check procedure will be in place at the start of the main trial, and we anticipate it will remain in place until the VRT algorithm is refined (as per pre-specified adaptations during the trial period) such that it appears accurate and safe.

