Outcome assessment: The ED diagnosis will have been elicited from ED providers by study personnel as a forced choice diagnosis. For the primary outcome, a correct “ED SOC Diagnosis” requires that the “Adjudicated Final Diagnosis” is the same diagnostic category. The VRT diagnosis will be assigned automatically by the online algorithm in real-time.

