2.2 Outcomes

2.2.1 Aim 1 (Trial Outcome): Measure the impact of VRT on diagnosis and initial management

Hypothesis 1: The VRT pathway will yield more correct diagnoses by the end of the ED index visit than the standard care (ED provider-determined) pathway.

Primary outcome 1: Six-Category Diagnosis Accuracy (all, VRT vs. SOC). Total proportion of correct diagnoses made by VRT vs. SOC among subjects with 30-day adjudicated final diagnoses (the gold standard) categorized in one of six possible diagnosis categories (3 peripheral, 1 central, 1 medical/other, 1 non-diagnosis).

Statistical Analysis Plan 1:

Primary analysis 1: A generalized linear model with a log link will be used for comparing the true positive rates (TPRs) of VRT and SOC. Without additional covariates, the model-based score test is equivalent to a Pearson Chi-square test for unpaired data. The regression model will assess the influence of demographic and key clinical variables as exploratory subgroups. Generalized estimating equation (GEE)¹⁶¹ method will be used to account for clustering effects by hospital site or provider. VOG non-completers are excluded pre-randomization (randomization occurs post-VOG for all patients).

Specifically, define $D_i = 1$ if the 30-day adjudicated final diagnosis for the i th subject is categorized in one of six possible diagnosis categories (3 peripheral, 1 central, 1 medical/other, 1 non-diagnosis). Define a test variable as

$$X_{Test} = \begin{cases} 1 & \text{for VRT} \\ 0 & \text{for SOC} \end{cases}$$

Define $Y_i(\text{VRT}) = 1$ if the index VRT diagnosis for the i th subject is the same as his/her 30-day adjudicated final diagnosis and $Y_i(\text{VRT}) = 0$ otherwise. Similarly, define $Y_i(\text{SOC}) = 1$ if the ED SOC Diagnosis for the i th subject is the same as his/her 30-day adjudicated final diagnosis and $Y_i(\text{SOC}) = 0$ otherwise.

The TPR, over the total proportion of correct diagnoses, is defined as follows

$$TPR(X_{Test}) = P[Y_i(X_{Test}) = 1 | D_i = 1], \quad X_{Test} = 0, 1.$$

Define the regression model as

$$\log TPR(X_{Test}) = \alpha_0 + \alpha_1 X_{Test} + \overline{\alpha_i} \cdot \overline{X_i}$$

where $\overline{X_i}$ is a vector of additional subgroup variables or other covariates to be explored for assessing the influence of demographic and key clinical variables described in the secondary analysis.

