Secondary analysis 1: For each of the six possible diagnosis categories (3 peripheral, 1 central, 1 medical/other, 1 non-diagnosis), define the gold standard =1 if the 30-day adjudicated final diagnosis is the corresponding category and 0 otherwise. Define test positive respectively for “Index VRT Diagnosis” and “ED SOC Diagnosis” if the diagnosis is the corresponding category and 0 otherwise. Estimate sensitivity, specificity, predictive values and likelihood ratios accordingly for “Index VRT Diagnosis” and “ED SOC Diagnosis”. Between-arm comparisons will be performed by the generalized linear model with a log link as described in primary analysis 1a.

Tertiary analysis 1: Subgroups and covariates:

The regression model is

$$\log TPR(X_{Test}) = \alpha_0 + \alpha_1 X_{Test} + \overline{\alpha_l} \cdot \overline{X_l}$$

where $\overline{X_l}$ is a vector of additional subgroup variables or other covariates to be explored for assessing the influence of demographic and key clinical variables described below.

1) Potential Subgroups:

- a. AVS-Only Group: using only patients with acute (continuous) vestibular syndrome >24hr.
- b. Younger-Patient Group: using only patients 49 years of age or younger (i.e., 18-49).
- c. Women-Minority Group: using only patients self-identifying as female, minority, or Hispanic.
- d. NIHSS 0 Group: using only patients with an NIH stroke scale score of zero at ED index visit.
- e. Stands-Independently Group: using only patients who stand without assistance or support.
- f. Normal Hearing Group: excluding any patient with hearing loss (new or old).
- g. Non-AICA Group: excluding any patient with an AICA-territory stroke diagnosis.
- h. Pre-Treatment Group: using only patients with results obtained prior to anti-vertigo meds.
- i. VRT Definite-Only Group: using only “definite” VRT diagnoses (excluding VRT-E cases).
- j. Specific ED-Only Diagnosis Group: using only “definite” ED diagnoses (excluding ED O2).
- k. Neuro-otologic Diagnosis Group: using only patients with peripheral or central diagnoses.

2) Potential Covariates:

- l. Site: JH vs. UI vs. UM.
- m. Age (ordinal): 18-49, 50-59; 60+ years.
- n. Age (continuous): for each year.
- o. Sex: female vs. male.
- p. Race/Ethnicity: minority vs. non-Hispanic white.
- q. Symptom Onset (ordinal): 0-24, 25-48, 49-72, >72 hours.
- r. Symptom Onset (continuous): time from symptom-onset for each hour.
- s. Symptom Type: vertigo vs. dizziness vs. unsteadiness.

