Total diagnosis accuracy optimized VRT vs. SOC using 30-day adjudicated final diagnoses categorized in one of six diagnosis categories (3 peripheral, 1 central, 1 medical/other, 1 non-diagnosis). We will use "Optimized VRT Diagnosis" and "ED SOC Diagnosis" compared to the "Adjudicated Final Diagnosis" based on ED index visit and 30-day follow-up clinical assessments. Optimized VRT diagnoses will be run using the final (end-of-trial) version of the VRT algorithm. Only SOC-arm subjects are used for this outcome, as VRT patient results will have been used to optimize the algorithm during the trial. VRT diagnoses in the SOC arm (algorithm not run during the trial), will be assigned based on the final, optimized algorithm; for this purpose, the ED SOC diagnosis will be assigned as the VRT diagnosis for algorithm results in the VRT-E group. This outcome measure reflects the estimated diagnostic accuracy of the end-of-trial automated algorithm.

5. Central-Peripheral Diagnosis Accuracy (all, VRT vs. SOC)

Total diagnosis accuracy VRT vs. SOC using 30-day adjudicated final diagnoses categorized as central (stroke, posterior fossa mass lesion, encephalitis, demyelinating disease, etc.) vs. non-central (includes peripheral vestibular, medical, psychiatric, non-diagnoses, etc.).

6. Central Discharge Proportion (central subgroup only, VRT vs. SOC)

Total discharge proportion of central causes VRT vs. SOC. Central causes determined based on 30-day adjudicated final diagnosis.

7. Peripheral Admission Proportion (peripheral subgroup only, VRT vs. SOC)

Total admission proportion of peripheral causes VRT vs. SOC. Peripheral causes determined based on 30-day adjudicated final diagnosis.

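### Subgroup (i) drops equivocal cases using a label that only the VRT arm carries, so its between-arm contrast favours VRT if those cases are harder; (j) is also a post-randomisation filter and is under-defined

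*SAP*

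**What the plan says.** SAP 2.2.1 defines the outcome by arm: agreement of the index VRT diagnosis with the adjudicated final diagnosis in the VRT arm, and agreement of the ED diagnosis with it in SOC. The model is log-link with an arm indicator (X_Test), and "The regression model will assess the influence of demographic and key clinical variables as exploratory subgroups". Without covariates, "the model-based score test is equivalent to a Pearson Chi-square test for unpaired data".

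Tertiary analysis 1 repeats that model and lists potential subgroups. Item (i) keeps definite "VRT diagnoses (excluding VRT-E cases". Item (j) keeps definite "ED diagnoses (excluding ED O2". Protocol 9.2.1 carries the same list. Neither document says how (i) applies to SOC patients or how (j) applies to VRT patients.

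On who has a VRT label, Protocol 5.1 says of the control arm that "no VOG automated interpretation or summary report will be generated". SAP exploratory outcome 4 says: "VRT diagnoses in the SOC arm (algorithm not run during the trial), will be assigned based on the final, optimized algorithm". That assignment is made for outcome 4 only and is not linked to subgroup (i).

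On the ED diagnosis, SAP 2.1 says: "The ED diagnosis will have been elicited from ED providers by study personnel as a forced choice diagnosis". No arm is named. I found no definition of the label O2 in either document.

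**The concern.** A subgroup keeps the benefit of randomisation when membership is fixed before allocation, or is at least determined in the same way in both arms. Age and sex meet that test. The VRT-equivocal label does not: it is a result produced after randomisation in one arm. Apply (i) literally and the VRT arm loses its equivocal patients, while the SOC patients who would have been called equivocal stay in.

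The documents give reason to expect equivocal patients to be harder. Under Protocol 5.1 the ED provider takes over their diagnosis and a neurology consultation is requested. Protocol section 7 (Diagnostic Process) says patients whose earlier ear or eye-movement disease could mislead the test are deliberately sent to the equivocal result. Equivocal is also not one of the six outcome categories. If these patients are less often correct, a definite-only contrast shows VRT ahead even where the arms are equal, and that is the direction of Hypothesis 1.

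**Working it through.** **Inputs from the documents.** 113 per arm, 1:1 allocation, alpha 0.05, power 80%, design accuracies 90% and 75%, and an overall ED accuracy of about 56% (SAP 2.1 and 2.3).

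**Inputs that are assumptions.** The share removed, *f*, and the accuracy of the removed cases, *q*. The documents give neither.

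**Reproducing the plan's figure.** For 90% vs 75%, two-sided 0.05 and 80% power, the usual two-proportion formula gives 99.5, so 100 per arm. With continuity correction it gives 112.5, so 113, as in Table 3. The other five rows of Table 3 also reproduce with that formula. I therefore use 113 per arm and a two-sided 0.05 test.

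**Expected gap with equal arms.** Let true accuracy be P in both arms. After removal from VRT only:

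- accuracy of kept VRT cases = (P − f·q)/(1 − f)
- SOC accuracy stays at P
- false gap = f(P − q)/(1 − f), which is zero when q = P

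**Scenario A: 85% correct in clear cases, 50% in equivocal cases, both arms.** P = 0.50f + 0.85(1 − f).

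| f | SOC accuracy (P) | VRT kept | False gap (points) | False-positive rate |
|---|---|---|---|---|
| 10% | 81.5% | 85% | 3.5 | 0.106 |
| 20% | 78.0% | 85% | 7.0 | 0.253 |
| 30% | 74.5% | 85% | 10.5 | 0.448 |

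Worked row, f = 20%: n = 113 × 0.8 = 90.4 in VRT and 113 in SOC. SE = √(0.85×0.15/90.4 + 0.78×0.22/113) = 0.0541. The gap divided by its SE is 0.070/0.0541 = 1.29. The rejection probability is Φ(1.29 − 1.96) + Φ(−1.29 − 1.96) ≈ 0.253. Simulating the Pearson test itself gives about 10, 24 and 42% for the three rows, so the normal approximation is slightly high at f = 30%.

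**Scenario B: both arms at the SAP's 75% overall, 50% in equivocal cases.** Rates are from 100,000 simulated Pearson tests.

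| f | SOC | VRT kept | False gap (points) | False-positive rate |
|---|---|---|---|---|
| 10% | 75% | 77.8% | 2.8 | 7.6% |
| 20% | 75% | 81.3% | 6.3 | 18.5% |
| 30% | 75% | 85.7% | 10.7 | 44% |

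**Range over the assumptions, f = 20%.**

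- P = 75%, q = 25%: 87.5% vs 75%, a gap of 12.5 points against the 15-point design effect; rate 62%.
- P = 75%, q = 0 (every equivocal case scored as no match): 93.8% vs 75%; rate 97%.
- P = 56%, q = 25%: 63.8% vs 56%; rate 20%.
- q = P: gap 0, rate about 5%.

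**Same filter in both arms.** If the same *f* and *q* apply to VRT and SOC, the expected gap is 0 and the rejection rate is about 5%, except where kept accuracy reaches 100%.

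**The case against.** The strongest reply has four parts.

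**One-sided exclusion is inferred.** The SAP gives (i) one line and does not say that SOC stays unfiltered. That is true, but the stated rule needs a label that SOC patients lack during the trial. The only place that gives them one is a different outcome. Applied as written, the rule can act only on VRT.

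**The size is assumed.** This stands. The rate runs from 5% to 97% across plausible inputs. The share is also unclear because Protocol 5.1.3 lets the expert reviewer change an equivocal result to a specific condition, in the VRT arm only, and Protocol 9.1 bases the primary outcome on the result actually delivered. Neither document says whether VRT-E means the label before or after that review.

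**Subgroup (j).** A reader might infer that (j) is the mirror image of (i), biased towards SOC. The documents do not support that. Taking O2 to mean a non-specific diagnosis is a guess. The ED diagnosis is elicited without any stated restriction by arm, so the VRT arm may have one too. If so, providers there will have seen the VOG result, and the filter would still depend on arm, with unknown direction.

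**The items are exploratory.** They are potential subgroups in a tertiary analysis, and the phase 3 decision rule in SAP 2.3 uses total accuracy and costs. This limits the consequence. It does not remove the bias: an exploratory label warns about multiplicity, not about a contrast that is systematically off.

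**Conclusion.** The point holds for (i). The rule as written excludes on a post-randomisation label specific to the VRT arm, inside a VRT-vs-SOC model, and favours VRT whenever equivocal cases are less often correct than the rest. Under the stated assumptions the false advantage is 3.5 to 10.5 points with false-positive rates of about 11 to 45% (Scenario A), or about 8 to 44% (Scenario B). These figures illustrate the mechanism and do not predict what the trial will show. It would be too strong to say that the contrast must show a difference between equal arms, because the gap vanishes if equivocal cases are no harder.

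For (j), what holds is narrower: it filters on a diagnosis made after randomisation, one of its terms is undefined, and its use in the VRT arm is unspecified. No direction of bias can be claimed.

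The primary analysis, its alpha and the sample size are untouched.

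**What to change.** In SAP 2.2.1 and in the matching list in Protocol 9.2.1, report (i) and (j) as within-arm descriptive accuracy with the share excluded, and make no X_Test comparison for either. Define ED O2, and state whether ED diagnoses are recorded in the VRT arm.

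If a between-arm version of (i) is wanted, define the exclusion by the raw equivocal flag, before expert review, from one algorithm version run on the index VOG in both arms. That recording precedes randomisation in every patient. Two limits should be written in:

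- The run planned for exploratory outcome 4 covers SOC only, so it does not supply this comparison. The same version must also be run on stored VRT-arm recordings.
- Protocol 9.1 restricts algorithm changes to results from the VRT or observational arms. A flag from the final version is therefore in-sample for VRT and out-of-sample for SOC, which is itself an imbalance to report.

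The cost is a few sentences in each document and either the loss of the between-arm test for these exploratory subgroups or a small extra re-run. No new data are needed. The change should be made before the unmasked analysis.

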Total diagnosis accuracy “as computed in real time,” algorithm-only VRT diagnosis vs. SOC using 30-day adjudicated final diagnoses categorized in one of six possible diagnosis categories (3 peripheral, 1 central, 1 medical/other, 1 non-diagnosis). We will use “Index VRT Diagnosis” and “ED Physician Diagnosis” compared to the “Adjudicated Final Diagnosis” based on ED index visit and 30-day follow-up clinical assessments. This

outcome measure reflects the weighted average diagnostic accuracy of the various versions of the automated algorithm as it would have been absent human double-check during the course of the trial.

6. *Optimized Six-Category Within-Subject Accuracy* (SOC arm only, optimized VRT vs. SOC)

Total diagnosis accuracy optimized VRT vs. SOC using 30-day adjudicated final diagnoses categorized in one of six possible diagnosis categories (3 peripheral, 1 central, 1 medical/other, 1 non-diagnosis). We will use “Optimized VRT Diagnosis” and “ED Provider Diagnosis” compared to the “Adjudicated Final Diagnosis” based on ED index visit and 30-day follow-up clinical assessments. Optimized VRT diagnoses will be run using the final (end-of-trial) version of the VRT algorithm. Only SOC-arm subjects are used for this outcome, as VRT patient results will have been used to optimize the algorithm during the trial. VRT diagnoses in the SOC arm (algorithm not run during the trial), will be assigned based on the final, optimized algorithm; for this purpose, the ED SOC diagnosis will be assigned as the VRT diagnosis for algorithm results in the VRT-E group. This outcome measure reflects the estimated diagnostic accuracy of the end-of-trial automated algorithm.

7. *Expert VOG Six-Category Diagnosis Accuracy* (all, expert VOG vs. SOC)

Total diagnosis accuracy adjudicated expert VOG diagnosis vs. SOC using 30-day adjudicated final diagnoses categorized in one of six possible diagnosis categories (3 peripheral, 1 central, 1 medical/other, 1 non-diagnosis). We will use “Index VOG Diagnosis” and “ED Physician Diagnosis” compared to the “Adjudicated Final Diagnosis” based on ED index visit and 30-day follow-up clinical assessments. This outcome measure reflects the theoretical maximum diagnostic accuracy performance (i.e., expert level) of any future algorithms.

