- t. Symptom Severity: VSS-SF score.
- u. Vestibular Syndrome: episodic positional vs. episodic spontaneous vs. acute continuous.
- v. Hearing Loss: new hearing loss vs. no new hearing loss.
- w. Vascular Risk Severity (continuous): ABCD2 (0-7).
- x. Neurologic Severity (continuous): NIHSS (0-42).
- y. Ataxia Severity (continuous): SARA score (0-40).
- z. Stroke size (continuous): greatest dimension in millimeters.
 - aa. Stroke location: none, hemispheric-only, posterior fossa (with or without hemispheric).
 - bb. Confounded: unconfounded vs. potentially confounded (medications or illnesses).
 - cc. Comorbidities (continuous): Charlson Comorbidity Index (0-56).

Secondary outcomes 1.1-1.2: Diagnosis accuracy for different category groupings and comparisons; the following accuracy comparisons are considered:

1. Expert VOG Six-Category Diagnosis Accuracy (SOC arm, expert VOG vs. ED SOC)

Total diagnosis accuracy adjudicated expert VOG diagnosis vs. ED SOC using 30-day adjudicated final diagnoses categorized in one of six diagnosis categories (3 peripheral, 1 central, 1 medical/other, 1 non-diagnosis). We will use “Index Expert VOG Diagnosis” and “ED SOC Diagnosis” within the SOC arm based on ED index visit and 30-day follow-up clinical assessments. This within-subject comparison reflects the current potential accuracy of expert VOG-based tele-diagnosis and the targeted maximum diagnostic accuracy performance (i.e., expert level) of future automated algorithms.

2. Stroke-No Stroke Diagnosis Accuracy (all, VRT vs. SOC)

Total diagnosis accuracy VRT vs. SOC using 30-day adjudicated final diagnoses categorized as stroke vs. no stroke (including peripheral vestibular, medical, psychiatric, or other central neurologic causes such as multiple sclerosis, traumatic brain injury, epilepsy, or anticonvulsant toxicity).

Statistical Analysis Plan Secondary Outcomes 1.1-1.2: A generalized linear model with a log link will be used for comparing the true positive rates (TPRs) of VRT and SOC. Without additional covariates, the model-based score test is equivalent to a Pearson Chi-square test for unpaired data. The regression model will assess the influence of demographic and key clinical variables as exploratory subgroups. Generalized estimating equation (GEE)¹⁶¹ method will be used to account for clustering effects by hospital site or provider.

2.2.2 Aim 2 (Trial Outcome): Measure the impact of VRT on initial diagnostic work-up costs

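### SAP Secondary 1.1 compares two diagnoses of the same patients, but the only test described for it is an unpaired, between-arm one

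*SAP*

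**What the plan says.** SAP section 2.2 heads Secondary 1.1 with "SOC arm, expert VOG vs. ED SOC" and explains: "This within-subject comparison reflects the current potential accuracy of expert VOG-based tele-diagnosis". Each standard-care patient therefore contributes two correct/incorrect scores against one final diagnosis.

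The only method text is a paragraph covering Secondary 1.1 and 1.2 together. It begins "A generalized linear model with a log link will be used for comparing the true positive rates (TPRs) of VRT and SOC", describes the test with "the model-based score test is equivalent to a Pearson Chi-square test for unpaired data", and says that the GEE "method will be used to account for clustering effects by hospital site or provider". These sentences repeat Primary analysis 1. The indicator defined there ("Define a test variable as") equals 1 for VRT and 0 for SOC, and no other indicator is defined. Secondary analysis 1 presents the same model as a between-arm tool: "Between-arm comparisons will be performed by the generalized linear model with a log link as described in primary analysis 1a".

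In Protocol section 9.2 the expert outcome was number 7 and was defined over "all, expert VOG vs. SOC". The SAP narrowed it to the SOC arm and made it within-subject, but kept the protocol's method wording. That protocol paragraph also covered outcomes 4 (VRT versus MRI) and 6 (optimized VRT versus SOC), both within one arm. They are now Exploratory 2 and 4 in the SAP, which states no test for them.

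**The concern.** Two scores on one patient are generally correlated. An unpaired test takes the variance of their difference as the sum of two independent variances and drops the covariance. If the correlation is positive, the standard error and interval are too wide and power is lost. If it is negative, the interval is too narrow and the type I error exceeds 5%.

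The stated contrast does not fit either. Read as trial arm, the VRT/SOC indicator is constant within the SOC arm. It could be relabelled as expert versus ED, but the SAP does not do this, and relabelling alone would still leave the unpaired test.

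At stake are the p-value and confidence interval of one of only two secondary accuracy outcomes that the SAP retains. As written, they depend on a choice made after the fact.

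**Working it through.** **Inputs.** SAP section 2.3 gives 90% versus 75%, alpha 0.05, power 80% and 113 per arm. These are the planning values for the primary outcome; neither document gives any for Secondary 1.1, so I borrow them with p1 = 0.90 (expert), p2 = 0.75 (ED) and n = 113 pairs. Phi is an assumption throughout.

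**1. The plan's own figure.** Two-sided, without continuity correction: n0 = [1.960·√(2·0.825·0.175) + 0.842·√(0.09 + 0.1875)]² / 0.15² = 99.5, so 100. With the correction: (n0/4)·[1 + √(1 + 4/(n0·0.15))]² = 112.5, so 113. The stated figure reproduces, and it belongs to an unpaired comparison.

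**2. Possible range of phi.** The proportion with both diagnoses correct lies between 0.65 and 0.75. Phi = (p11 - 0.675)/√(0.09·0.1875) = (p11 - 0.675)/0.1299, so phi lies between -0.19 and 0.58.

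**3. Standard errors.**
- Unpaired: √[(0.09 + 0.1875)/113] = 0.0496.
- Paired: √[(0.2775 - 2·phi·0.1299)/113]. At phi 0.3 this is √(0.1996/113) = 0.0420, a ratio of 1.18.

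**4. Power and size at 113 pairs.** Simulated, 200,000 to 400,000 draws per case, pooled Pearson against McNemar without continuity correction. Null rejection is at 75%/75%.

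| phi | unpaired/paired SE | power, unpaired | power, McNemar | null rejection, unpaired | null rejection, McNemar |
|---|---|---|---|---|---|
| -0.19 | 0.92 | 84% | 79% | 7.3% | 5.0% |
| -0.1 | 0.96 | – | – | 6.2% | 4.9% |
| 0 | 1.00 | 86% | 86% | 5.0% | 4.9% |
| 0.2 | 1.11 | 89% | 93% | 2.9% | 5.1% |
| 0.3 | 1.18 | 90% | 96% | 1.9% | 5.2% |
| 0.4 | 1.26 | 92% | 98% | 1.2% | 5.3% |

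At phi -0.19 the unpaired test's higher power is bought with inflated type I error.

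**5. Fewer pairs.** Protocol section 9.1 analyses only patients who complete the essential diagnostic steps, and 226 = 2 × 113 leaves no allowance for loss. The losses below are assumed. Power, unpaired versus McNemar, at phi 0.2, 0.3 and 0.4:
- 100 pairs: 84% vs 90%, 86% vs 93%, 88% vs 96%.
- 90 pairs: 79% vs 86%, 81% vs 90%, 83% vs 94%.

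**6. Larger gaps.** At 95% versus 75% (113 pairs, phi 0 to 0.3) and at 90% versus 56%, both tests exceed 99% power.

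**7. Worked examples, 113 patients.**
- Near the planned rates: expert 102 correct, ED 85, with 20 expert-only and 3 ED-only correct. Difference 17/113 = 15.0 points. Unpaired SE 0.0493, 95% CI 5.4 to 24.7, p = 0.0028. Paired SE √[(23 - 17²/113)]/113 = 0.0400, 95% CI 7.2 to 22.9, McNemar chi-square 17²/23 = 12.6, p = 0.0004. The conclusion is the same; the interval is tighter.
- Smaller gap: 13 expert-only and 4 ED-only correct (83.2% versus 75.2%). Pearson p = 0.140; McNemar p = 0.029 (exact 0.049). Here the conclusion changes.

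**8. Does the GEE sentence repair it?** Only if both records of a patient share a cluster. With site as cluster they do, but in simulation (both rates 80%, phi 0 to 0.4) an uncorrected sandwich Wald test rejects a true null about 26% of the time with 3 sites and 15% with 5. A patient cluster gives about 5%.

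**The case against.** The strongest reply is that the paragraph does not end with the Pearson sentence. That sentence states an equivalence, and its reference to unpaired data can be read as a condition. The GEE follows. Patients are nested in sites, and in providers if both diagnoses are assigned to the treating ED provider, so a cluster-robust variance would contain the within-patient covariance. With both records in the cluster, no provider effect and an uncorrected sandwich test, simulated power at phi 0.2, 0.3 and 0.4 is 92%, 96% and 98% with 28 providers (an assumed number), almost the same as McNemar.

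This stands as far as it goes: the losses in the table apply if the unpaired test is used. It does not clear the SAP. The expert reader is not the ED provider, and nothing says where the expert's record belongs. Without a small-sample correction, the same approach rejects a true null about 6% of the time with 28 providers, 8% with 14 and 15% with 5 sites.

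It is also fair to say that positive correlation is the likelier case, so the error is probably conservative, and that Exploratory 2 and 4 lack a test in the SAP rather than having a wrong one. Both points limit the weight of the finding without removing it.

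**Conclusion.** The concern holds and is minor. The SAP declares a within-subject comparison, and the only test it describes for it is unpaired. If that test is used with 113 pairs at 90% versus 75% and phi of 0.2 to 0.4, the cost is 4 to 6 power points. With 90 pairs it is 7 to 12. At negative phi the error rate rises to at most about 7%. All of this rests on assumed values of phi and, for the smaller samples, assumed losses.

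The pairing defect does not reach the primary analysis, Secondary 1.2, the 113-per-arm calculation, any point estimate, or the part of the Phase III rule that uses point estimates. The unpaired wording is correct for the between-arm analyses; the fault lies in carrying it over to Secondary 1.1.

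**What to change.** Give Secondary 1.1 its own method text:
- Use two records per SOC patient, with an indicator for expert VOG versus ED in place of the VRT/SOC variable.
- Specify McNemar's test with a paired confidence interval for the difference in accuracy, or a log-link GEE with patient as the cluster.
- If provider clustering is kept, place both of a patient's records in the same provider cluster and state a small-sample correction, for example a K/(K-1) variance factor with a t reference on K-1 degrees of freedom.

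The last item matters only if provider effects are appreciable. In a null simulation with 112 pairs, phi 0.3 and assumed provider ICCs of 0, 0.05 and 0.10, McNemar rejected 5.1%, 5.7% and 6.6% of the time with 28 providers, and 5.3%, 6.6% and 8.2% with 14. The corrected provider-cluster GEE stayed at 4.5% to 4.8%.

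Use the same paired approach for Exploratory 2 and 4, and leave the between-arm contrast in place for Secondary 1.2. The cost is one or two sentences in the SAP before analysis. No new data are needed.
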